## 14.3 Ethics Committee (EC) / Institutional Review Board (IRB)

Investigators must submit this clinical investigation protocol to their respective Ethics Committee (EC) and or Institutional Review Board (IRB) and obtain the EC's/IRB's written approval before being allowed to conduct and participate in the study. Each Investigator is responsible for fulfilling any conditions of approval imposed by their respective EC/IRB, such as regular reporting, study timing, etc. Investigators will provide the Sponsor or its designee with copies of such approvals and reports.

## 14.4 Informed Consent Form (ICF)

The Sponsor will provide a template informed consent form (ICF) to each study site for EC/IRB submission. The template may be modified to suit the requirements of the individual study site but the Sponsor must pre-approve all changes to the ICF prior to initial submission to the EC/IRB.

Each Investigator or assigned designee must administer this approved ICF to each prospective study subject and obtain the subject's signature or a legally-approved designee's signature along with the date of consent prior to enrollment in the study. The ICF must be obtained in accordance with the applicable guidelines on 21 CFR 50, 54 and 56, the Declaration of Helsinki, EN ISO 14155 or local regulations and laws, whichever represents the greater protection of the individual. Subjects must be informed about their right to withdraw from the study at any time and for any reason without sanction, penalty, or loss of benefits to which the subject is otherwise entitled and also be informed that withdrawal from the study will not jeopardize their future medical care. A copy of their signed ICF must be given to each subject enrolled in the study. The institutional standard subject consent form does not replace the Connected Catheter study ICF.

## 14.5 Case Report Forms (CRFs)

The Sponsor will provide standardized case report forms (CRFs) for each individual subject. The CRFs will be electronic via a 21 CRF Part 11 compliant EDC, and will be used to record study data, and are an integral part of the study and subsequent reports.

The electronic CRFs for individual subjects will be provided by the Sponsor via a web portal. After the data have been monitored and submitted, corrections will be initiated via a data query to

be completed by study site personnel. This data query will be done electronically via the web portal. Electronic CRFs must be approved and signed by the Investigator in the appropriate spaces provided using his/her electronic signature.

Electronic Case Report Forms (eCRFs) will be used to collect all subject data during the course of the study. eCRFs must be fully completed for each subject and electronically signed by the Investigator when complete. The eCRFs should be a complete and accurate record of subject's data collected during the study according to EN ISO 14155:2011 standard. Regulations and Good Clinical Practice (GCP) guidelines require that Investigators maintain information in the study subject's medical records that corroborate data collected on the eCRFs. To comply with these regulatory requirements, the following information should be maintained:

1. Medical history/physical condition of the subject before involvement in the study sufficient to verify protocol entry criteria.
2. Dated and signed notes on the day of entry into the study including the study Investigator, study name, subject number assigned and a statement that consent was obtained.
3. Dated and signed notes from every subject appointment with reference to the CRFs for further information, if appropriate (for specific results of procedures and exams).
4. Information related to adverse events.
5. Subject's condition upon completion of or withdrawal from the study.
6. Discharge summaries/procedure reports.

## 14.6 Records

Each Investigator must maintain the following accurate, complete, and current records relating to the conduct of the study investigation. The final responsibility for maintaining such records remains with the Investigator. These records include, but not limited to:

- All signed agreements;
- IRB/EC approval letter(s);
- Signed ICF;
- Records of AEs, including supporting documents;
- Records of protocol deviations, including supporting documents
- Records showing receipt, use and disposition of all investigational devices, including:
  - Date, quantity, model and lot or serial numbers of devices received,
  - Name of person(s) who received, used or disposed of each device,
  - The number of devices returned to the Sponsor and the reason(s) for return;
- All correspondence related to the study;
- Records of each subject's case history, including study-required CRFs, signed ICF, all relevant observations of AEs, the condition of each subject upon entering and during the course of the investigation, relevant medical history, the results of all diagnostic testing, etc.;

- Study personnel visit log;
- Signature authorization and delegation log; and,
- Any other records that applicable regulation requires to be maintained.

#### 14.7 Reports

Table 14-1 lists those reports that are the investigator's responsibility to deliver to the Sponsor. Each study investigator must follow the EC/IRB reporting requirements for their respective site. If applicable regulations or EC/IRB requirements mandate stricter reporting requirements than those listed, the stricter requirements must be followed.

**Table 14-1: Reports Required from Investigators to Sponsor**

Type of Report	Prepared by PI for	Notification Time Frame
UADE	Sponsor, EC/IRB	Within 10 working days of knowledge
Death	Sponsor, EC/IRB	Written reports (e.g., via e-mail) within 48 hours
SAE	Sponsor	Within 10 working days of knowledge
	EC/IRB, if required	Per IRB requirement
Device malfunction with clinical sequelae	Sponsor EC/IRB, if required	Within 48 hours via written communication. Return the device to sponsor within 48 hours.
Serious protocol deviations (e.g., ICF not obtained, to protect the life or physical well-being of a subject in an emergency)	Sponsor EC/IRB, if required	Within 5 working days of knowledge Per IRB requirement
Withdrawal of EC/IRB approval	Sponsor	Within 5 working days of knowledge
Annual progress report	Sponsor, EC/IRB	Annually
Final report	Sponsor, EC/IRB	Within 3 months of study completion or termination
Note: Each IRB/EC may require more stringent reporting requirements than those listed in this table.		

## 14.8 Sponsor Responsibilities

Spinal Singularity, Inc. is the Sponsor of this study. The Sponsor's responsibilities in the study include:

- Selecting the Principal Investigator(s), all clinical investigators and study sites, and other consultants or personnel (e.g., monitors) who participate in the study.
- Provide study protocol, device, and GCP training to participating study sites, in quantities sufficient to support study activities, per agreements executed with the study sites.
- Select all qualified clinical Investigators and study sites and other consultants or personnel (e.g., monitor) who participate in the study.
- Provide financial support to each study site.
- Follow/promote all regulatory standards per appropriate regulations for study sites, core laboratories, and other participants, and ensure compliance by periodically monitoring sites.
- Ensure completion of site monitoring of clinical data at each clinical study site.
- Retain ownership of all clinical data generated in this study, and control the use of the data for appropriate purposes only.
- Review and approve publication of study results in the literature.

### 14.8.1 Confidentiality

All information and data sent to the Sponsor concerning subjects or their participation in this study will be considered confidential according to HIPAA regulations. Data used in the analysis and reporting of this evaluation will be used in a manner without identifiable reference to the subject. Investigators will consent to visits by Sponsor's staff and its authorized representatives, as well as by the U.S. FDA or any other local governmental body, to review the study subjects' medical records, including any test or laboratory data that might have been recorded on diagnostic test media.

### 14.8.2 Amending the Investigational Study Protocol

Neither any Investigator nor the Sponsor will modify this Clinical Investigational Protocol without first obtaining concurrence of the other in writing. All changes to the Clinical Investigational Protocol must be submitted to the EC/IRB for review and approval. Any change that would require alteration to the ICF must receive approval from the applicable EC/IRB prior to implementation. Following approval, any Investigational Protocol amendment must be distributed to all protocol recipients at the site.

### 14.8.3 Protocol Deviations

A protocol deviation/violation is generally an unplanned excursion from the protocol that is not implemented or intended as a systematic change. An Investigator failed to perform tests or examinations as required by the protocol or failures on the part of study subjects to complete scheduled visits as required by the protocol, would be considered protocol deviations. These types

of deviations are reported to the sponsor and in accordance with the IRB policy.

A Protocol Deviation CRF must be completed by the site for each study protocol deviation (e.g., failure to obtain informed consent, enrolling a subject who does not meet inclusion / exclusion criteria, not performing required testing, missed follow-up window, etc.). An Investigator must notify the Sponsor and the reviewing EC/IRB of any deviation from the Study Protocol that was done to protect the life or physical well-being of a subject. Such notice should be given as soon as possible, but no later than five (5) working days after the emergency occurred.

#### **14.8.4 Site Noncompliance and Nonperformance**

Repeat serious protocol deviations will be closely monitored. If excessive deviations or a failure to reduce deviations are noted, the Sponsor reserves the right to suspend study enrollment at that site until a sufficient system is in place at the site to reduce further deviations.

After a site completes all required approvals and training, a Site Initiation Visit (SIV) will be conducted as a final check of the site readiness. If a site is not able to enroll its first subject 3 months after “Ready to Enroll” status, the Sponsor may elect to terminate the investigational site and allocate the slot to another candidate site.

The Sponsor reserves the right to terminate an investigational site from the study for any of the following reasons including, but not limited to:

1. Failure to obtain Informed Consent
2. Failure to report safety events (i.e. Adverse events)
3. Repeated protocol violations
4. Repeated failure to complete Electronic Case Report Forms
5. Failure to enroll an adequate number of subjects

#### **14.8.5 Device Accountability**

The Gen 2 Connected Catheter Systems allocated for investigational site use will be stored in a secured area until use. Each site will be responsible for tracking the receipt and disposition of all investigational Gen 2 Connected Catheter System devices. The unused Gen 2 Connected Catheter Systems must be returned to the Sponsor at the end of the study.

#### **14.8.6 Sponsor Reporting Responsibilities**

Table 14-2 lists those reports that are the Sponsor's responsibility and timelines to report to the IRB. If applicable regulations or IRB requirements mandate stricter reporting requirements than those listed, the stricter requirements must be followed.

**Table 14-2: Sponsor Reporting Responsibilities**

Type of Report Report Prepared For	Sponsor Reporting Responsibilities	
	Reporting Time Frame	Report Prepared For
Unanticipated Adverse Device Effect (UADE)	Investigators, IRBs	Written - Within 10 working days from the time the Sponsor first learns of the effect.
Withdrawal of IRB Approval or other action on part of the IRB that affects the study	Investigators, IRBs	Written – Within 5 working days.
Device Recall	Investigators, IRBs	Written – Within 30 working days.
Inappropriate Informed Consent	IRB	Investigator's report submitted within 5 working days of notification
Study Closure	Investigators, IRBs	Within 10 days
Final Report	Investigators, IRBs	Final report - within 6 months of study closure

## 15 STUDY ADMINISTRATION

### 15.1 Monitoring Procedures

It is the responsibility of the study Sponsor to ensure that proper monitoring of this investigation is conducted. Appropriately trained personnel, appointed by the study Sponsor, will complete any monitoring that is done. The monitoring will be the responsibility of Sponsor study personnel with an address as listed in the title page of this document. Monitor(s) will ensure that the investigation is conducted in accordance with:

- The signed Investigator's Agreement
- The Investigational Plan
- Appropriate laws and regulations
- Any conditions of approval imposed by the reviewing EC/IRB and/or other regulatory agencies

The clinical study will be monitored according to the guidelines summarized below. The Sponsor may choose to perform random inspections throughout the study as an element of quality assurance. Investigators will allow auditing of their clinical investigation procedures.

A study specific Monitoring Plan is created and implemented to standardize monitoring activities across centers and ensure human subject protection and verify data integrity. The monitors will receive study specific and SOP training prior to conducting any monitoring visits. Study monitors are selected based on their training, qualifications and experience to monitor the progress of an investigation. Study monitors may be Sponsor's employees or representatives. This study monitoring will include a site qualification, study initiation, interim, and close out visits. All study monitors will be required to follow the Sponsor's monitoring plan and monitoring standard operating procedures (SOPs).

The study monitoring will be executed by a Sponsor representative.

### **15.1.1 Monitoring Visit**

The following factors will be taken into account when determining the frequency of the monitoring visits: subject accrual rate at each center, total number of subjects enrolled at each center, and Clinical Investigation Protocol compliance at each center. It is anticipated each site will be monitored at least once upon the completion of the follow-up visits for all enrolled subjects at the study site. Monitors will require direct access to subjects' medical records pertinent to the study (and study inclusion criteria), study management documents, regulatory documents and Subject Informed Consent documents, as well as other potential applicable records not listed here.

Monitors may ensure the clinical investigators have and continue to have staff and facilities to conduct the clinical investigation safely and effectively. Monitors may conduct the following monitoring activities throughout the study:

- Verification that the current IRB-approved informed consent was signed and dated by each subject prior to participating in the study required procedures.
- Verification of documentation in the subject's record that informed consent was signed prior to initiation of the study procedures and that a copy of the signed and dated consent was provided to the subject.
- Source documentation verification by reviewing the eCRFs against source documentation for accuracy and completeness of information.
- Verification that the Investigational Devices are being used according to the Clinical Investigation Protocol, Instructions for Use and, all malfunctions / IFU deficiencies are reported. as required.
- Verification that subjects met study enrollment criteria.
- Confirmation that the study is being conducted according to the Clinical Investigation Protocol and applicable regulations.
- Verification that study deviations are documented and reported.
- Verification that the procedures for recording and reporting adverse events to the sponsor are followed.
- Ensuring proper error correction.
- Verification of training documentation of all study personnel participating in study related activities.

- Reviewing all correspondence and regulatory documents, including confirmation of IRB-approved Clinical Investigation Protocol or amendments.
- Resolution of outstanding issues and completion of assigned tasks will be documented by the monitors.

Each monitoring visit will be documented via a monitoring report and follow-up letter. The follow up visit letter will be sent to the Investigator to document issues identified, corrective actions and if applicable preventive actions. At subsequent visits the issues resolved will be documented in this letter to demonstrate resolution. Monitoring visits will be conducted by trained monitors and designees. The Monitoring Plan identifies the frequency of monitoring and training requirements of the monitors.

### **15.1.2 Study Closure**

Study closure is defined as a specific date that is determined by study completion and/or regulatory requirements have been satisfied per the Clinical Investigation Protocol (CIP) and/or by decision of the Sponsor or IRB. Study closure visits will be conducted at all enrolling clinical sites in order to review record retention requirements with site personnel. A telephone contact may take the place of a study closure visit if appropriate (e.g., low subject enrollment, recent monitoring visit, etc.)

## **16 CLINICAL TRIAL OVERSIGHT**

### **16.1 Safety Monitoring**

Evaluation and adjudication of safety data (e.g. serious adverse events, all deaths, etc.) will be performed on an ongoing basis by the Independent Research Monitor. The Independent Research Monitor for this study will be [name], MD. Data and reports will be reviewed and adjudicated pursuant to the guidelines outlined in this clinical investigation protocol and [name] will have full authority to stop the study in accordance with ethical practices and stopping rules.

In addition to these reports, data will be aggregated for review and analysis periodically. These reports will be shared with the Independent Research Monitor and the monitor will be offered the opportunity to provide insight or input into any observable trends in the data.

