## 11.9 Anticipated Adverse Events

The following is a list of potential anticipated adverse events that may occur while using the Connected Catheter.

1. Asymptomatic Bacteriuria
2. Autonomic Dysreflexia (for individuals with spinal cord injury)

3. Bladder or Urethral Perforation (False Passage)
4. Bladder or Urethral Spasms
5. Change in frequency or urgency to urinate
6. Discharge or Cloudy Urine
7. Discomfort
8. Dysuria (Painful Urination)
9. General Fever
10. Genitourinary pain
11. Hematuria (Blood in Urine)
12. Injury to the Lower Urinary Tract (LUT) and/or Genitals
13. Interference with Sexual Activity
14. Part or All of the Connected Catheter Becoming Temporarily Stuck in the LUT
15. Scarring of LUT
16. Systemic Infection
17. Urinary Incontinence
18. Urinary Retention
19. Urethral Stricture
20. Urinary Tract Infection
21. Urinary Tract Inflammation or Irritation

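### A site may take 10 working days to report a non-fatal SAE to the sponsor, and nothing sets a time or route for it to reach the monitor who is to adjudicate it

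*Combined protocol and SAP*

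**What the plan says.** Section 16.1 (Safety Monitoring) states that evaluation and adjudication of safety data, with SAEs and deaths as examples, "will be performed on an ongoing basis by the Independent Research Monitor". It adds that this person "will have full authority to stop the study in accordance with ethical practices and stopping rules".

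The reporting times are in Section 14. In 14.7, "Table 14-1 lists those reports that are the investigator's responsibility to deliver to the Sponsor". In Table 14-1:

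- **SAE and UADE:** to the sponsor "Within 10 working days of knowledge".
- **Device malfunction with clinical sequelae:** to the sponsor "Within 48 hours via written communication".
- **Death:** to the sponsor and EC/IRB in writing, also within 48 hours.

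Onward reporting is in 14.8.6, where "Table 14-2 lists those reports that are the Sponsor's responsibility and timelines to report to the IRB". Table 14-2 has the sponsor pass a UADE to investigators and IRBs "Within 10 working days from the time the Sponsor first learns of the effect". It has no row for an SAE that is not a UADE.

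Section 13.3 adds periodic review by the independent research monitor and a DSMB, with no interval. Both are to help decide whether a temporary halt is needed.

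**The concern.** A reviewer with authority to stop a study can act only on events that have arrived. A site that complies fully with Table 14-1 can leave the sponsor, and so the monitor, unaware of a serious device injury for up to two weeks, while men at as many as four sites have devices inserted or exchanged every week. The time from sponsor to monitor is then unlimited on paper.

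The order of the deadlines is also hard to defend. A malfunction with a minor clinical consequence is due in 48 hours. A serious injury from a device that worked as designed may wait 10 working days.

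The UADE route would not normally catch this case. Section 11.9 lists bladder or urethral perforation and systemic infection as anticipated. Under 11.3, a serious case would then usually be an SAE and not a UADE, unless its severity or incidence went beyond what was foreseen.

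**Working it through.** **Calendar length of the deadline.** Ignoring holidays, 10 working days end 14 calendar days after a weekday on which the site learns of the event, 13 after a Saturday and 12 after a Sunday. The device is replaced at least every 7 days and the Test Phase is 28 days (Synopsis). So 14 days is 14/7 = 2 device cycles and 14/28 = 50% of the Test Phase. With weekly exchanges, every man with an exchange still to come reaches the next one inside 14 days. Inside 2 days, 2/7 = 29% do.

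**Search for a route to the monitor.**

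| Place | What it gives | Does it set a time to the monitor? |
|---|---|---|
| 11.8 | All AEs entered on an eCRF | No; no entry deadline |
| 13.3 | Periodic monitor and DSMB review | No; no interval |
| 14.7 | Stricter regulatory or EC/IRB times prevail | No; monitor not mentioned |
| Table 14-2 | UADE to investigators and IRBs | No; no SAE row |
| 15.1.1 | Site visit at least once, after follow-up is complete | No |
| 16.1 | Ongoing adjudication; periodic aggregate reports | No time stated |

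**UADE chain to other investigators.** Table 14-1 plus Table 14-2 allows 14 + 14 = 28 days. With 48 hours at the first step it is 2 + 14 = 16 days.

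**Illustration of exposure.** The documents give no accrual rate and no SAE risk, so both are assumed.

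- Treated men: 24, of whom 16 continue (8.8).
- Insertions: one each at first, then four in the Test Phase (one at its start and three exchanges, 9.4). Total 24 + 16 × 4 = 88.
- Accrual: 12 months less 7 weeks per subject, 52 − 7 = 45 weeks. Insertions then span 45 + 4 = 49 weeks.

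Flat-rate counts:

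- First insertions: 24/45 × 2 = 1.07 in 14 days; 24/45 × 2/7 = 0.15 in 2 days.
- All insertions: 88/49 × 2 = 3.59 in 14 days; 88/49 × 2/7 = 0.51 in 2 days.

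A simulation agrees. It assumes uniform entry, two thirds of men using the device for 35 days and one third for 7, and SAE time uniform over device use. It counts insertions in other men after the first SAE. At SAE risks of 2% to 20% it gives about 1.0 first and 3.6 total insertions in 14 days, against about 0.15 and 0.5 in 2 days. If accrual took only 19 weeks (a faster rate chosen to show the range, with no basis in the documents), the figures are 2.1 to 2.5 and about 8, against 0.3 to 0.4 and 1.0 to 1.2.

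**Events at stake.** The same simulation gives the expected SAEs per trial that fall between day 2 and day 14 after the event that would prompt a pause:

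| Assumed SAE risk | Pause on 2nd SAE, 45 wk | Pause on 2nd SAE, 19 wk |
|---|---|---|
| 2% | 0.001 | 0.003 to 0.004 |
| 5% | 0.01 | 0.03 |
| 10% | 0.06 | 0.13 to 0.14 |
| 20% | 0.17 to 0.18 | 0.40 |

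With a pause on the first SAE, the range at risks of 2% to 5% is about 0.006 to 0.07 across both accrual assumptions.

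**The case against.** Several points on the other side stand.

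- A reader might infer that 16.1 and Table 14-1 contradict each other. They do not: 16.1 never gives its ongoing review a time, and 10 working days is a ceiling. Nor is the monitor's absence from the two tables an error in itself, since one table covers reports to the sponsor and the other reports to the IRB.
- A reader might infer that the monitor is the main safeguard because primary safety has no formal test. The absence of a test concerns the final analysis. The DSMB also reviews data (13.3), the sponsor can suspend enrolment at a site with excessive deviations (14.8.4) or terminate the study (9.7.1.2), and the sponsor or IRB can close it (15.1.2).
- The eCRF is a second way for the sponsor to learn of an event, and stricter outside rules override the table.
- The treating site knows at once and can withdraw its own subject. Men keep a removal tool and the clinic number (7.2), and Test Phase exchanges are supervised (8.3).
- Faster notice triggers nothing by itself. Any gain depends on the monitor choosing to pause.

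These reduce the gap but do not close it. None gives a time for a non-fatal SAE to reach the person named to adjudicate it, and local protection does not help men at other sites.

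**Conclusion.** The gap is real. A fully compliant site can leave the sponsor and monitor unaware of a non-fatal SAE or a UADE for 12 to 14 calendar days, and no further time to the monitor is stated. Correcting this is a worthwhile, low-cost improvement. It is not a flaw that undermines the study.

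The numerical gain is small. The insertion counts are exposures, and a reader should not take them as injuries prevented. Expected SAEs avoided are under 0.1 per trial at risks of 5% or less, and then only if the monitor would pause. At 10% to 20% with a second-event pause they are about 0.06 to 0.4. All of this rests on assumed accrual and SAE risk.

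A reader might also scale the figures up to the 60 treated subjects mentioned in 10.3. That number conflicts with the 36 enrolled, 24 entering tolerability screening and 16 evaluable in 8.8, so it is no basis for a larger estimate.

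Separately, 16.1 refers to stopping rules that the protocol nowhere defines. This is a drafting point and adds nothing to the timing issue.

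**What to change.** 1. **Table 14-1, SAE and UADE rows:** set the recipient and time to *Sponsor and Independent Research Monitor, in writing, within 48 hours of knowledge*. Leave the EC/IRB times as they are, which means splitting the UADE row in two.
2. **Table 14-1, Death row:** add the monitor as a recipient; the 48 hours already applies.
3. **Section 14.7:** amend the introductory sentence so that SAEs, UADEs and deaths go to the monitor as well as the sponsor.
4. **Section 16.1 (secondary):** define the stopping rules or delete the reference to them. A numerical pause trigger is optional and is for the sponsor and monitor to decide.

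No change to the DSMB's role is needed. Section 13.3 has it assist the sponsor, and nothing places it under the monitor.

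The cost is a shorter SAE and UADE reporting time for sites, though one they must already meet for deaths and for malfunctions with clinical sequelae. No new staff or committee is required. It is a protocol amendment, so 14.8.2 requires written concurrence between sponsor and investigators and EC/IRB approval.
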